Subjects will receive conservative standard of care treatment plus two ITU treatments (week 0 and week 4) on the affected CET (figure 2) using the ultrasound therapy device. Treatments will be up to 10 minutes in duration. A 2, 4, and 8 week follow up period will be included to monitor the effects of the therapy post treatment. A 12 and 24-26 week telephone assessments for the primary objectives will also be included. Telephone assessments will consist of the subjects answering the survey questions over the phone.

Subject self-assessments will be conducted before the treatment phase and during the follow-up period. Physical exams will be completed by a physician. Physical therapy will be completed by a therapist. ITU treatment and diagnostic ultrasound will be performed by Guided Therapy personnel as shown in the full schedule of events (Appendix 1).

[figure not shown]

Figure 2: Treatment Area

SELECTION OF SUBJECTS**Planned number of subjects**

The study population will consist of up to 25 subjects with unilateral CET tendinosis defined as pain lasting more than 3 months with little or no improvement following conservative standard of care alone.

The selection of suitable subjects will be made according to the inclusion and exclusion criteria described in the following sections.

Inclusion Criteria

1. Subjects who are in general good health and are willing to cooperate and participate by following study requirements for the duration of the study, and to report any adverse symptoms immediately;
2. Subjects who have provided written and verbal informed consent;
3. At time of enrollment subjects are between the ages of 21 and 65 years
4. Subjects literate in English and able to complete all patient self-assessment questionnaires;

5. Subjects is willing to refrain from beginning any additional treatment during the duration of the study;
6. Subjects is willing to refrain from changing physical activity during the duration of the study;
7. Subjects diagnosed with unilateral CET tendinosis defined as pain lasting more than 3 months with little or no improvement following conservative standard of care alone.
8. Subjects with BMI ≤ 35 or at the discretion of the PI.
9. Subjects must be able to sit in a chair with their arm on an appropriate table for the treatment and diagnostic ultrasound imaging.
10. Subject must be able and willing to complete the at home therapy regimen.

Exclusion Criteria

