
If a subject meets all the inclusion/ exclusion criteria, they will be enrolled onto the study, issued a subject number and an X-ray will be scheduled.

Visit 1 and 3: (Weeks 0 and 4) Study treatments

1. Record AEs, con meds and other events
2. Administer PRTEE-A questionnaire (Appendix 2)
3. Subject self-assessment questionnaire (Appendix 3)
4. Focused Physical Evaluation
5. Diagnostic Ultrasound images taken
6. ITU treatment, and VAS assessment of treatment tolerability.
7. Physical Therapy will be performed as described (Appendix 4 – Visit 1 only)
8. Home Cold Pack & Stretching Program review and Log (Appendix 6-A and 6-B)

Visit 2, and 4: (Weeks 2 and 8) Diagnostic Ultrasound, Self-Assessments, Physical Examination

1. Record AEs, con meds and other events;
2. Administer PRTEE-A questionnaire (Appendix 2)
3. Subject self-assessment questionnaire (Appendix 3)
4. Diagnostic Ultrasound image taken;
5. Home Cold Pack & Stretching Program review and Log (Appendix 6-A and 6-B)

Phone/Online Interviews at 3 and 6 months post treatment

1. Record AEs, con meds and other events;
2. Follow-up phone interview PRTEE-A verbally administered (Appendix 2).
3. Subject self-assessment questionnaire (Appendix 3)

STUDY TREATMENT

ITU will be performed by a trained technologist, using a clinical prototype (Ulthera FDA cleared in Sept. 2009) GEN II or GEN III designed Guided Therapy Systems, LLC. Mesa, AZ USA (Appendix 7-A).

Subjects will be treated seated with their arm resting on a structure that is comfortable for the subject and technologist. Transdermal application of ITU therapy: An average energy up to 3 joules (0.5 to 3 J) will be administered to the affected CET tendon longitudinally until the maximum number of lines (12) are reached. Each line will include individual thermal zones, less than 1 mm³ in volume, centered at a depth between 2 – 6 mm, up to 2 mm apart (figure 3).

[figure not shown]
[figure not shown]

Figure 3. Zone pitch, and depth. Tendo

Treatment pattern:

Acoustic Coupling Gel will be applied every 3-5 lines.

Figure 3-1. Zone pitch, and depth.

The study treatment will be a 10 minute session using the ultrasound therapy device with coupling gel. Subjects will be treated seated with their arm resting on a structure that is comfortable for the subject and technologist.

DIAGNOSTIC ULTRASOUND IMAGING

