Diagnostic Ultrasound Imaging will be performed by a trained Sonographer using the Spark® Imaging System, manufactured by Ardent Sound, Inc., Mesa, AZ USA (Appendix 7-B)

Subjects will be imaged seated with their arm resting on a structure that is comfortable for the subject and sonographer.

PolySonic® or AquaSonic® Gel will be applied by the sonographer as required to maintain adequate acoustic coupling. (Appendix 7-C)

1

[figure not shown]
Images will be preserved with the following notations:

- Protocol ID
- Right vs. Left CET Tendon
- Treated vs. Untreated

Long Axis and Short Axis (if necessary) images will be stored at the Sonographer's discretion, to demonstrate and track the applicable anatomy/pathology in the peri-CET area.

Sonographer will also measure the thickness of the CET tendon in each applicable image.

Sonographer will scan the contralateral CET tendon in the same manner noting the change in the tendon (Right v. Left) and (Treated v. Untreated).

Common Extensor Tendon
Figure 4: representative long axis ultrasound images

Outcome measures

Subjects will complete subject reported outcome measures at 0, 2, 4, 8, 12, and 24 weeks and will undergo a focused physical examination and diagnostic ultrasound at 0, 2, 4, and 8 weeks. Adverse events will be recorded at each visit. Treatment tolerability will be assessed immediately after each treatment using the Visual Analog Scale for Pain (VAS) or Universal Pain Assessment Tool (Appendix 3-B). The VAS will be used for 2 different assessments: 1. Pain related to physical activity of the symptomatic arm before treatments and at follow-up visits and phone surveys. 2. Pain tolerance of the therapy treatment. Each of these assessments will be documented and evaluated separately.

Aim 1: reported outcomes

The principal aim of this study is to assess the efficacy of treatment and time course of response to treatment using validated subject reported outcome measures assessing pain, function and level of activity. Subjects will complete validated subject reported outcome questionnaires assessing pain, function and level of activity prior to initiating treatment and at

0, 2, 4, 8, 12, and 24 weeks after starting treatment (Appendix 2 and 3A).

Clinical Pain and Treatment Tolerance will be assessed using the Visual Analog Scale for Pain (VAS) or Universal Pain Assessment Tool (Appendix 3-B).

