Appendix 1- Calendar of Events

Procedures	Visit 0 Recruitment -14 to 0 Days	Visit 1 Baseline Assessment Week 0	Visit 2 Week 2	Visit 3 Week 4	Visit 4 Week 8	Phone Survey Week 12	Phone Survey Week 24	Responsibility
PI/C, eligiblity paperwork, exam for inclusion criteria	X							PI/Clinical Coordinator (CC)
X-Ray Scheduled	X							PI or Outside
Ultrasound Imaging		X	X	X	X			GTS
ITU Treatment		X		X				GTS
Focused Physical Exam & Clinical Grading for Epicondylitis severity		X	X	X	X			PI or CC
Subject Patient Rated Tennis Elbow Evaluation		X	X	X	X	X	X	Panelist Week 2-8 / PI or CC Weeks 12 and 24
Self-Assessment Questionnaires: Satisfaction & Improvement		X	X	X	X	X	X	Panelist Week 2-8 / PI or CC Weeks 12 and 24
Physical Therapy		X						PI or CC
Home Heat/Cold & Stretching Program Review		X	X	X	X			PI or CC
Telephone Survey						X	X	PI or CC

GUIDED THERAPY SYSTEMS, CONFIDENTIAL

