Appendix 3-A; Self Reported Outcome Measures

SROM 1.

Compared to your initial visit:

- I feel BETTER OFF than before treatment
- I feel THE SAME as before treatment
- I feel WORSE than before treatment

SROM 2.

Compared to your initial visit, describe your heel pain now:

- I have NO PAIN
- I have LESS PAIN than before the treatment regimen
- I have THE SAME PAIN as before the treatment regimen
- I have MORE PAIN than before the treatment regimen

SROM 3.

What percent improvement in heel pain have you experienced since starting the study?

- None
- 1 to 25%
- 26 to 50%
- 51 to 75%
- 76 to 99%
- 100%

SROM 4.

How do you rate your heel pain since the start of the study treatment?

- All better
- Much better
- Slightly better
- Unchanged
- Worse

SROM 5.

What percent improvement in overall daily function including work and/or recreational activities have you experienced since starting the study?

- None
- 1 to 25%
- 26 to 50%
- 51 to 75%
- 76 to 99%
- 100%

SROM 6.

Regarding the treatment that you received:

[figure not shown]
- I am TOTALLY SATISFIED with the treatment
- I am SATISFIED with MINOR RESERVATIONS with the treatment
- I am SATISFIED with MAJOR RESERVATIONS with the treatment
- I am DISSATISFIED with the treatment

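### The SROM improvement and satisfaction form is scheduled at Week 0, before any ITU, where it cannot serve as a baseline for a named primary endpoint

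*Protocol*

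**What the plan says.** Several parts of the Protocol bear on when the form is completed.

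- **Visit list.** Under "Visit 1 and 3: (Weeks 0 and 4) Study treatments", the Appendix 3 self-assessment is item 3. Item 6 is "ITU treatment, and VAS assessment of treatment tolerability".
- **Appendix 1, Calendar of Events.** The row "Self-Assessment Questionnaires: Satisfaction & Improvement" is marked at Week 0 and at every later contact.
- **Outcome measures.** "Subjects will complete subject reported outcome measures at 0, 2, 4, 8, 12, and 24 weeks". Aim 1, in the same section, cites Appendices 2 and 3A and asks for completion before treatment starts as well as at those weeks.
- **Study Outline.** "Subject self-assessments will be conducted before the treatment phase and during the follow-up period". This is general wording that does not name SROM.

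On content, Appendix 3-A has six items. SROM 1 asks for a comparison with the initial visit, with options such as "I feel BETTER OFF than before treatment". SROM 6 opens with "Regarding the treatment that you received".

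On status, Assessment of Efficacy lists SROM improvement and satisfaction among the primary endpoints. It labels the form 3-B, although the form itself is headed 3-A and 3-B is the pain scale.

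On analysis, the Protocol's before-and-after sentence under Statistical analysis names PRTEE and VAS (or the Universal Pain Assessment Tool). The SAP compares VAS pain and PRTEE with baseline and does not mention SROM.

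**The concern.** PRTEE asks about the past week and the pain VAS about pain levels, so both have a meaningful value before treatment. SROM is a transition and satisfaction form, and it has no meaningful value until something has been done to the subject. Aim 1 nevertheless places it among the pre-treatment measurements from which efficacy and time course are to be assessed.

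Two things are at stake. If the schedule is followed, uninterpretable answers will certainly be recorded in a named primary measure. In addition, a Week 0 column will be on file with no rule for its use, in a study that takes the Week 0 value as baseline for its other self-reported measures. Someone could then treat a column of null answers as the before value and test against it.

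**Working it through.** **1. Timing.** The calendar and Aim 1 identify SROM explicitly at Week 0. The Visit 1 list puts Appendix 3 (item 3) ahead of ITU (item 6). No section exempts 3-A from that visit.

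**2. What each item can return before the first ITU** (Appendix 3-A).

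| Item | Reference point | Null option | Worsening option | Week 0 content |
|---|---|---|---|---|
| SROM 1 | initial visit / before treatment | yes | yes | same |
| SROM 2 | initial visit / before the regimen | yes | yes | same |
| SROM 3 | start of study | yes (none) | **no** | none |
| SROM 4 | start of study treatment | yes | yes | unchanged |
| SROM 5 | start of study | yes (none) | **no** | none |
| SROM 6 | treatment received | no | not a change item | no valid answer |

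The reference points differ between items. The initial visit could mean Visit 0, which the calendar places up to 14 days earlier, or Visit 1. SROM 2, 3 and 4 also ask about the heel, in an elbow trial.

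**3. Planned use.** Neither document specifies any SROM analysis, so there is no SROM figure to reproduce. The sample size of 25 (two-sided alpha 0.05, 80% power) comes with no endpoint, effect size or SD. It is not tied to SROM and does not change under the fix.

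**4. Consequence if Week 0 were used as the comparator.** With a constant null baseline, a paired test reduces to an exact sign test on the non-null follow-up answers. For SROM 3 and 5 every non-null answer points to improvement, so with k such answers:

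p = 2 × 0.5^k

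- k = 5: 2 × 0.5^5 = 0.0625
- k = 6: 2 × 0.5^6 = 0.031
- k = 8: 2 × 0.5^8 = 0.0078

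Six of 25 (24%) is therefore enough for p < 0.05. Let q be the chance that a subject reports improvement without any ITU effect. The documents give no q, so the range is an assumption. The chance of p < 0.05 is P(X ≥ 6) with X ~ Binomial(25, q):

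| q | SROM 3 or 5 |
|---|---|
| 5% | 0.1% |
| 10% | 3.3% |
| 20% | 38% |
| 30% | 81% |
| 40% | 97% |

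For SROM 1, if non-null answers without an ITU effect split evenly between better and worse, the same test rejects at most 2.5% of the time for q from 5% to 50%. Counting worse answers matters: 6 better and 1 worse gives p = 2 × (1 + 7)/2^7 = 0.125, and 8 better and 2 worse gives p = 2 × (1 + 10 + 45)/2^10 = 0.109.

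**The case against.** The strongest reply is that the harm needs an analysis nobody has planned. That is correct: before-and-after comparison is stated only for PRTEE and VAS, so a Week 0 SROM tick changes no planned estimate.

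The reply also rules out two stronger readings that a reader might infer.

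- *The form cannot be answered at Week 0.* This is strictly true only of SROM 6. SROM 1 to 5 have null options and can be ticked; they just carry no baseline information. If the initial visit means Visit 0, even a null answer to SROM 1 or 2 is not fully forced.
- *Any before/after use shows a false effect.* A constant baseline creates no effect if follow-up answers are null too, and SROM 1, 2 and 4 allow worsening. The clear risk is confined to SROM 3 and 5.

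The even split assumed for SROM 1 may be generous. All subjects also receive standard care and physical therapy, and the Appendix 4 exercise sheet expects relief in about 4 to 6 weeks in most cases. Against that, eligibility requires little or no improvement on conservative care, so the size of any drift is unknown.

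A further objection stands in full. Improvement unrelated to ITU comes from having no untreated comparison group, and dropping the Week 0 form does not cure it. An exact interval for 6 of 25 runs from 9.4% to 45.1%, and even 1 of 25 has a lower bound of 0.1%. An interval that excludes zero is therefore not evidence that ITU worked.

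Finally, the Study Outline sentence is general, and the Visit 1 item cites Appendix 3 as a whole, which includes the pain scale. Neither identifies SROM by itself; the calendar and Aim 1 do.

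**Conclusion.** The scheduling defect is real and rests on the text alone: a named primary measure is collected before the first ITU, when one of its six items has no valid answer and the other five hold no baseline information. If the schedule is followed, up to 25 satisfaction answers about a treatment not yet given would be recorded. It is up to 25, not at least 25, because enrolment is capped there.

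The inferential risk is conditional. It arises only if Week 0 is used as a comparator, which neither document plans, and it is clearest for SROM 3 and 5. The p = 0.031 assumes 25 respondents, 6 non-null answers and none worse. The higher false-positive rates depend on assumed values of q. The documents do not support saying that the planned analyses are biased by this form. The correction is worth making because it is specific and nearly free, and it keeps invalid answers out of a primary measure.

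**What to change.** 1. Exempt Appendix 3-A from Week 0 in Aim 1 and Outcome measures, in the Visit 1 list and in the Appendix 1 calendar. Visits 1 and 3 share one list, so limit the exemption to Visit 1. Name the form by title, because the appendix labels disagree.
2. Keep PRTEE and the pain VAS (3-B) at Week 0, and give the VAS its own calendar row, which it lacks now. Leave the general pre-treatment sentence in the Study Outline in place for these two measures.
3. State in the Protocol and SAP that SROM is summarised only as the response distribution at each post-treatment visit, with exact 95% confidence intervals and no Week 0 comparison. State also that it is not evidence of an effect caused by ITU.
4. Use one anchor in SROM 1 to 5, such as *before your first ultrasound treatment*, and correct heel pain to elbow pain in SROM 2 to 4 in the same edit.

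The cost is an edit to the schedule, the form and one analysis paragraph, with the usual IRB approval of the amendment. It removes a form from one visit, adds no burden for subjects and leaves the sample size unchanged.

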Appendix 3-B – Subject Self-Assessment Questionnaire, continued:

VAS: Visual Analog Scale for Pain or Universal Pain Assessment Tool.

UNIVERSAL PAIN ASSESSMENT TOOL

This pain assessment tool is intended to help patient care providers assess pain according to individual patient needs. Explain and use 0-10 Scale for patient self-assessment. Use the faces or behavioral observations to interpret expressed pain when patient cannot communicate his/her pain intensity.

GUIDED THERAPY SYSTEMS, CONFIDENTIAL
APPENDIX 4 – Clinical Site Physical Therapy

TBD along with clinical site and PI

Rehabilitation for Tennis Elbow

<http://www.hughston.com/lha/a.seven.htm>

Rehab For Tennis Elbow: The Super 7

The "super 7" exercises are an important part of treatment for tennis elbow. They are designed to strengthen the muscles in the forearm and increase flexibility through stretching. In most cases these exercises will help relieve elbow pain in about 4 to 6 weeks. Each stretching exercise is held for 15 seconds and repeated 2 or 3 times. This pattern is repeated 5 times a day.

Exercise 1. Stretching the muscles that extend the wrist (extensor muscles): Straighten the arm out fully and push the palm of the hand down so you feel a stretch across the top of the forearm.

Exercise 2. Stretching the muscles that flex the wrist (flexor muscles): straighten the arm out fully (palm side up), and push the palm downward to stretch. Strengthening exercises are performed twice a day following the stretching exercises. To perform these exercises, the patient sits in a chair with the elbow supported on the edge of a table or on the arm of the chair the wrist hanging over the edge. Use a light weight such as a hammer or soup can when performing the strengthening exercises. Repeat the exercises 30 to 50 times, twice a day, but do not push yourself beyond the point of pain.

Exercise 3. Strengthening wrist extensor muscles: Hold the weight in the hand with the palm facing down. Extend the wrist upward so that it is pulled back. Hold this position for 2 seconds and then lower slowly.

Exercise 4. Strengthening wrist flexor muscles: Hold the weight in the hand with the palm up. Pull the wrist up, hold for 2 seconds and lower slowly.

Exercise 5. Strengthening the muscles that move the wrist from side to side (deviator muscles): Hold the weight in the hand with the thumb pointing up. Move the wrist up and down, much like hammering a nail. All motion should occur at the wrist.

Exercise 6. Strengthening the muscles that twist the wrist (pronator and supinator muscles): Hold the weight in the hand with the thumb pointing up. Turn the wrist inward as far as possible and then outward as far as possible. Hold for 2 seconds and repeat as much as pain allows, up to 50 repetitions.

Exercise 7. Massage is performed over the area of soreness. Apply firm pressure using 2 fingers on the area of pain and rub for 5 minutes.

Appendix 5: Adverse Events Report
Sample AE Form

	AE Term	Serious Yes/ No	Severity, Relationship, Action Taken	Treatment of Event (if medication report CM)		Outcome
1			Severity: <hr/> Relationship: <hr/> Action taken: <hr/>	 01  02  03  04  05 (specify) <hr/>	Onset date: <hr/>	
2			Severity: <hr/> Relationship: <hr/> Action taken: <hr/>	 01  02  03  04  05 (specify) <hr/>	Onset date: <hr/>	

Severity	Relationship	Action Taken	Treatment of Event:	Outcome:
Mild	01= Not Related to treatment	01=None	01=None	01=Recovered
Moderate	02=Probably related to treatment	02=Treatment interrupted	02=Pharmacological Treatment (report CM)	02=Recovered w/ Sequelae
Severe	03=Definitely related to treatment	03=Treatment stopped	03=Non-Pharmacological Treatment 04=Hospitalization 05=Other	03=Recovering 04=Not Recovered 05=Fatal 06=Unknown

Investigator Signature: _____

Date: _____ / _____ / _____

GUIDED THERAPY SYSTEMS, CONFIDENTIAL

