Recording of adverse events will take place at all visits (see adverse event reporting form Appendix 5). Adverse events will be monitored throughout the study.

A treatment will not be administered if there is residual pain/discomfort experienced by the subject from the previous treatment.

ACCOUNTABILITY

Treatment administered to the subjects will be documented by the operator and tracked on the Case Report Form (CRF).

BREAKING THE CODE IN AN EMERGENCY

Treatment codes and allocation of treatment per subject will be accessible by the Principal Investigator of the study.

SAFETY MONITORING**ADVERSE EVENT**

An adverse event (AE) is any untoward medical occurrence in a subject, whether or not related to study product or study procedures. Adverse events include any occurrence that is new in onset, an exacerbation of a pre-existing condition and clinically significant laboratory values.

Exceptions

The following medical occurrences will not be reported as AEs;

- Pre-treatment Adverse Events; Any medical occurrence that occurs after informed consent, but before first administration of ITU treatment or first study procedure is considered as medical history and only recorded as an AE if it worsens during the study.
- Pre-existing medical condition; Events that occur with comparable frequency and severity to the subject's baseline condition are reported as medical history, not AEs unless they become exacerbated during the study.
- Pregnancy; This is not an AE however the PI must report any pregnancies to The Guided Therapy and the Institutional Review Board (IRB) for advice regarding the appropriate course of action.

Study Specific Expected Adverse Event

The following AEs are expected due to the use of these study products and/or procedures and for this specific study, they will not be regarded as AEs;

- Transient erythema may be expected as a result of the study treatment which is expected to subside after a few hours. This will not be recorded as an AE unless persistent after 24 hours.
- Subjects may experience mild-moderate tingling, warming, pain or discomfort during the study treatments. These will not be recorded as AEs unless persistent after 24 hours or if they increase to severe/unbearable sensations.

The following AEs may be expected due to the use of these study products and/or procedures and for this specific study, they will be regarded and recorded as AEs;

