- While trained personnel will administer the study treatments, there is a possibility for operator error that may result in a burn or high skin irritation response. These will be recorded as AEs.

SERIOUS ADVERSE EVENT

A serious adverse event (SAE) is an AE that results in any of the following outcomes: death; a life-threatening event; in-patient hospitalization; prolongation of existing hospitalization; a persistent or significant disability/incapacity; a congenital anomaly or birth defect. Any other important medical event may be considered a SAE when the event may jeopardize the subject and may require medical or surgical intervention to prevent one of the outcomes listed previously. Examples of such medical events include allergic bronchospasm requiring intensive treatment in an emergency room or at home, or convulsions that do not result in in-patient hospitalization. Just as a stable pre-existing condition is not an AE, hospitalisation for elective treatment (e.g. cosmetic or dental procedure) of a pre-existing condition that did not worsen from baseline is not an SAE.

SEVERITY AND RELATEDNESS OF ADVERSE EVENTS

An AE will be recorded only once, with the most extreme severity. Severities are defined as:

Mild	Awareness of symptoms which require minimal or no treatment and do not interfere with daily activity
Moderate	Discomfort or low level of interference which is enough to interfere with but not prevent daily activity and may require treatment
Severe	Interrupted or unable to perform usual daily activity and usually requires treatment.

The likelihood that the AE was related to the study product or study procedure is defined as;

Not Related	The AE is clearly due to an alternative cause, even if this cannot be definitely identified. Alternative causes include disease, concomitant medications, or environmental factors.
Uncertain	A connection between the AE and the study product or procedure cannot be ruled out with certainty.
Definitely	The AE is clearly related to the study product or procedure.

REPORTING OF ADVERSE EVENTS

All AEs will be recorded in the CRF and submitted to the IRB at the end of the study treatment phase and at the end of the regression phase. The site staff must maintain source documents to fully record all AEs.

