Additionally SAEs must be reported immediately to the IRB Title with 24 hours of the site staff becoming aware of the event. The contact details for reporting any expedited AE are given in the Contacts section of this protocol.

In the event that the percent of study related AEs is $\geq 25\%$ for a specific AE symptom, the IRB Title should be notified within 24 hours.

FOLLOW-UP OF ADVERSE EVENTS

If an AE is ongoing at the end of the study, follow-up will be performed until the AE has resolved. Follow-up may take the form of subject visits, a referral to another specialist, site telephone calls to the subject or letters from the treating physician.

The PI or designee must comply with the specific reporting requirement(s) of the ethics committee.

PREGNANCY

Females may not participate in this study if they are pregnant, breastfeeding, were pregnant or gave birth within the last three months or are planning a pregnancy during the course of the study.

GUIDED THERAPY SYSTEMS, CONFIDENTIAL

If the subject thinks they have become pregnant during the study it is important that they inform the study doctor immediately. If the subject becomes pregnant or thinks that they may be pregnant, they will be removed from the study.

STATISTICAL CONSIDERATIONS

SAMPLE SIZE CALCULATION

Up to 25 subjects will be enrolled onto the study to ensure a minimum of 25 subjects complete.

STATISTICAL METHODS

A sample size of 25 per protocol subjects will be required to demonstrate statistical significance (two-sided alpha=0.05; 80% power). Descriptive statistics will be calculated for comparison to the values noted in the existing literature.

MONITORING

The PI agrees that the site will permit, if required, study-related monitoring, audits, IRB/IEC review, and regulatory inspection(s), providing direct access to source data/documents.

Sponsor personnel, or their designees, may monitor the study. The monitor has the responsibility to familiarise the PI and the entire centre staff involved in the study with Therapy procedures. The monitor can visit the clinical study centre on a regular basis such as before the first subject has been enrolled, during the course of the study, and at study completion. The monitor must maintain the confidentiality of the study documents. Regular visits may be made to monitor clinical procedures throughout the study duration.

DATA HANDLING AND RECORD KEEPING

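### The protocol's relatedness scale and its AE form have different middle categories, so an Uncertain event cannot be recorded faithfully and the 25% related-AE rule can err in either direction

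*Protocol*

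**What the plan says.** The protocol section Severity and Relatedness of Adverse Events sets three levels, each judged against the study product or procedure:

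- The lowest level, Not Related, is worded "The AE is clearly due to an alternative cause, even if this cannot be definitely identified".
- The middle level, Uncertain, is worded "A connection between the AE and the study product or procedure cannot be ruled out with certainty".
- The highest level, Definitely, is worded "The AE is clearly related to the study product or procedure".

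The form in Appendix 5 offers three codes, each judged against treatment: "01= Not Related to treatment", "02=Probably related to treatment" and "03=Definitely related to treatment". The appendix labels it a sample, but Aim 3 (Assessment of safety and tolerability) points to it as the form in use: "Recording of adverse events will take place at all visits (see adverse event reporting form Appendix 5".

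The protocol section Reporting of Adverse Events contains a rule that begins "In the event that the percent of study related AEs is". It sets the limit at 25% or more for a specific AE symptom and requires notice to the IRB within 24 hours. It does not say which relatedness levels make an AE study related, or what the percentage is taken over. The SAP covers only pain reduction and the PRTEE score, and says nothing on adverse events.

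**The concern.** The top and bottom levels of the two scales correspond, but the middle ones do not. A link that cannot be excluded is a low bar; a probable link is a high one. An investigator who reaches the protocol's middle judgement finds no code on the form that says so.

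That middle level is likely to be used here. Every subject has a chronically painful elbow and receives ITU on top of standard care, and the example home programme stretches, strengthens and massages the same arm. New or worse elbow pain could come from the condition, the exercises or ITU. No untreated group gives a background AE rate, so attribution rests on the investigator's causality judgement.

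Safety is a stated objective, and the 25% rule is the only rate-based safety trigger in the documents. If the form cannot carry the judgement, the related-AE rate and the trigger inherit the error.

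**Working it through.** **1. The scales side by side.**

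| Level | Protocol body | Appendix 5 form |
|---|---|---|
| Lowest | Not Related | 01 Not Related |
| Middle | Uncertain | 02 Probably related |
| Highest | Definitely | 03 Definitely related |
| Judged against | study product or procedure | treatment |

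The severity grades (Mild, Moderate, Severe) agree in both places, so the mismatch is confined to relatedness.

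**2. Try each code for an Uncertain event.**

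- Code 01 requires a clear alternative cause under the protocol's definition. An event whose link cannot be excluded fails that test, so 01 contradicts the body and understates relatedness.
- Code 02 asserts a probable link that the investigator did not assert, so it overstates relatedness.
- Code 03 overstates it further.

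No code is faithful. The last row of the table adds a smaller gap: an event tied to a study procedure other than ITU is related under the body, but could be entered as 01 on a form that asks only about treatment.

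**3. The 25% rule.** The limit is a chosen threshold, so there is no derived figure to reproduce. Its denominator is not stated. Taking the planned 25 subjects as an assumption:

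- 0.25 × 25 = 6.25, so 7 subjects are needed.
- 7/25 = 28% meets the rule; 6/25 = 24% does not.
- Each recoded subject moves the rate by 1/25 = 4 points, so one subject alone changes the outcome only between 6 and 7.

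If the denominator is subjects treated to date, the count differs: with 4 treated, 1/4 = 25% already meets the rule.

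**4. Both directions in one example.** Suppose 8 of 25 subjects report the same symptom, 3 rated Definitely and 5 Uncertain. Let codes 02 and 03 both count as related.

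- Uncertain entered as 02: 8/25 = 32%, rule met.
- Uncertain entered as 01: 3/25 = 12%, rule not met.

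If the rule is meant to include Uncertain events, 32% is right and code 01 misses the notice. If it is meant to include only clear links, 12% is right and code 02 triggers a notice that was not intended. The documents do not say which is meant.

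**5. Size of the under-count, if it happens.** Let p be the chance that a subject has one given symptom not ruled out as related, and u the share of those entered as 01. The number counted is X ~ Binomial(25, p(1 − u)), and the rule fires when X ≥ 7. Both p and u are assumptions; neither is in the documents.

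| p | u = 0 | u = 0.25 | u = 0.5 |
|---|---|---|---|
| 0.30 | 65.9% | 32.5% | 7.0% |
| 0.40 | 92.6% | 65.9% | 22.0% |
| 0.50 | 99.3% | 88.4% | 43.9% |

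This table shows one direction only, and for u above 0 it supposes coding against the protocol's own definition.

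**The case against.** A reader might infer that the form pushes uncertain events out of the related count and so suppresses the 25% notice. The documents do not support that. Not Related is reserved for events with a clear alternative cause, so nothing forces code 01. On two ordered three-level scales the natural entry is the middle code, 02, which keeps the event among the related codes. Under-counting needs an investigator to depart from the protocol's definition.

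There are also backstops. Every AE, whatever its relatedness, goes to the IRB when the treatment phase closes and again when the regression phase closes. SAEs go within 24 hours with no causality condition. The 25% rule only brings notice forward, and no stopping rule is attached to it. The form is labelled a sample, and the final CRF may differ. Finally, the rule would be ambiguous even with matching scales, because its numerator and denominator are both undefined.

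All of this stands as a limit on the harm. It does not remove the point. Code 02 still misrecords the judgement, in the other direction. The protocol cites Appendix 5 as its reporting form, and the documents contain no other. The undefined numerator and denominator are a reason to widen the correction, not to omit it.

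**Conclusion.** The two scales contradict each other, and this rests on the text alone. An event judged Uncertain must be either overstated or understated on the form as printed.

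The consequence is two-way and moderate. The reported related-AE rate can be too high or too low, and the 24-hour notice can come when it was not intended or fail to come when it was. What is at risk is the rate and the timing of notice, not whether the IRB ever learns of an event. The boundary of 7 in 25 assumes full enrolment and subjects as the denominator. The example and the probabilities in the working rest on assumed rates, and show how far the count can move rather than how far it will. Sample size, endpoints and power are untouched. This should be corrected; it does not invalidate the trial.

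**What to change.** - Print the protocol's categories (Not Related, Uncertain, Definitely) on the Appendix 5 form, with its reference to study product or procedure in place of treatment.
- In Reporting of Adverse Events, state which categories count as study related for the 25% rule and for the AE tables. One option is every AE not rated Not Related; the choice is the sponsor's, as the documents do not dictate it.
- In the same sentence, state the denominator, for example subjects treated to date.

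The cost is a small form edit and a sentence or two in the protocol. Under the broad numerator the reported related-AE rate may be slightly higher. With subjects treated to date, the rule can also be met by very few events early on (1 of 4), which the sponsor should accept knowingly.
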